Appendix 2: 2-4 Month Convalescent EEG Assessment

- 1) Date_____
- Subject # _____
- 3) Person completing EEG assessment ____
- Subject's chronological age at EEG (in weeks)______
- 5) Postmenstrual age at birth (in weeks)
- 6) Duration of recording (minutes):
- 7) Quality of recording: Acceptable Unable to interpret

8) **Overall interpretation of the EEG**:

- a. Normal
- b. Abnormal
 - i. Abnormal with epileptiform features
 - ii. Abnormal with NO epileptiform features
 - iii. Hypsarhythmia (_classic; or _____modified)

9) Specific elements:

- a. Waking background
 - i. Well-organized
 - ii. Disorganized
 - iii. Abnormal slowing (_____Focal slowing; _____Diffuse slowing; __both)
 - iv. Persistent hemispheric asymmetry (which side is abnormal: __Left____Right)
 - v. No wakefulness recorded
- b. Sleep background
 - i. Drowsy-yes, no
 - ii. Stage 2- yes, no
 - iii. SWS- yes, no
 - iv. Sleep spindles present and normal
 - v. Sleep spindles absent
 - vi. Sleep architecture asymmetric or otherwise abnormal
 - vii. No sleep recorded
- c. Epileptiform abnormalities
 - i. Focal sharp waves or spikes
 - 1. Yes
 - 2. No
 - ii. Multifocal sharp waves or spikes
 - 1. Yes
 - 2. No
 - iii. Generalized spike-wave discharges
 - 1. Yes
 - 2. No
 - iv. Electrodecrements
 - 1. Present
 - 2. Absent
 - v. Recorded seizure
 - 1. Yes
 - 2. No
- d. Other abnormalities (specify; e.g. excessive beta)

The Warner Initial Developmental Evaluation of Adaptive and Functional Skills

(Warner IDEA-FS TM) • Version 11 • March 1, 2005 Michael E. Msall, Nancy Lyon, Melissa Gray, Kathleen DiGaudio

>>> How often can your child do the following without help?

2 = Sometimes, infrequent

1 = Never

I. Self-Care: Feeding

- 1. Easily drinks formula or breast milk
- 2. Easily swallows baby food
- 3. Chews solid food
- 4. Finger feeds
- 5. Eats using a spoon
- 6. Drinks from cup without a lid
- 7. Eats using a fork

II. Self-Care: Dressing

- 1. Holds arms up so you can put shirt on
- 2. Removes socks
- 3. Pulls pants down
- 4. Pulls up a zipper once it is started
- 5. Puts on t-shirt
- 6. Removes all clothes

III. Self-Care: Diaper Awareness

- 1. Indicates a wet diaper
- 2. Indicates a soiled diaper
- 3. Voids into potty chair or toilet
- 4. Sits on potty chair and has bowel movement

Subtotal Self-Care Domain (max=68)

IV. Mobility

- 1. Rolls both ways
- 2. Maintains sitting without support
- 3. Crawls short distance
- 4. Walks few feet with assistance (cruises)
- 5. Scoots or moves in wheelchair 10 feet
- 6. Walks 10 feet independently
- 7. Crawls up stairs
- 8. Gets on and off a chair
- 9. Walks up stairs with hand held

Subtotal Mobility Domain (max=36)

V. Communication

3 = Most of the time

- Understands words for people in immediate family (mommy, daddy) (R)
- 2. Demonstrates 2 syllable babbling (E)
- 3. Understands words for some common objects (R)
- 4. Gestures a social greeting (wave, blow a kiss) (E)
- 5. Carries out a 1 step oral request with gesture (pick up toy, cup) (R)
- Uses single words or signs to request or communicate (E)
- 7. Carries out a 1 step oral request without gesture (R)
- 8. Identifies one body part (R)
- 9. Identifies three or more body parts (R)
- 10. Points at pictures (R)
- 11. Has at least 10 words or 10 signs (E)
- 12. Combines words or signs to make needs known (E)
- 13. Names pictures (E)

Subtotal Communication Domain (max=52)

VI. Social Cognition

- 1. Plays "peek-a-boo", "patty cake", or "so big"
- 2. Looks for object dropped out of sight
- 3. Initiates social contacts with peers
- 4. Takes turns rolling a ball
- 5. Imitates another child
- 6. Recognizes familiar song
- 7. Starts mechanical toy or VCR/DVD/computer
- 8. Can pretend play with doll or toy
- 9. Turns pages in a book
- 10. Points at pictures when you read a story
- 11. Helps with simple household tasks

Subtotal Social Cognition Domain (max=44)

TOTAL SCORE

Total Items: 50 •• Maximum Score: 200

4 = All of the time

Subject #:_____

Appendix 4: Seizure/Epilepsy Follow-Up Telephone Questionnaire (Aim 1b)

Date	
Subject #	Subject age
Person completing questionnaire	

- 1. Did your child have seizures as a newborn (at any time during the first 28 days of life)?
 - a. Yes
 - b. No
 - c. Don't know
- 2. If your child was treated with medicine for neonatal seizures, did he/she ever stop taking this medicine?
 - a. Yes, before we left the hospital
 - b. Yes, after we left the hospital
 - c. No
 - d. Don't know
- 3. Your child was treated in the hospital for his or her seizures. After you went home from that admission, did your child ever have more seizures?
 - a. Yes
 - b. No
 - c. Don't know

[If answer to 3. Is "No", then indicate answer "a" for question 5 and end telephone survey. If yes, then continue.]

- 4. Let's talk about the seizure that happened after you went home from the hospital. When did your child start having seizures?
 - a. Age_____ months
 - b. Don't know
- 5. How often does your child have a seizure now?
 - a. No seizures since he/she was a newborn
 - b. Seizure-free for at least 6 months (# of months seizure-free _____)
 - c. 1 12 seizures per year (Fewer than 1 seizure per month)
 - d. 1-4 seizures per month
 - e. 5-30 seizures per month
 - f. >30 seizures per month (daily seizures)
 - g. Multiple seizures a day (2 or more seizures per day)
 - h. Don't know
- 6. Has your child ever been diagnosed with infantile spasms (a particular kind of epilepsy)?
 - a. Yes
 - b. No
 - c. Don't know
- 7. Is your child taking medication for seizures now?
 - a. Yes (Name of medication(s), if known _____
 - b. No
 - c. Don't know

Epilepsy questions for medical record review:

- 1. Did the child remain seizure-free after discharge from the admission during which neonatal seizures were diagnosed?
 - a. Yes.
 - b. No. Acute symptomatic neonatal seizures stopped, but unprovoked seizures began later.
 i. Date of first unprovoked seizure:
 - c. No. Seizures persisted without a convalescent period.
 - d. Don't know.

2. Postneonatal seizure semiology:

- a. No seizures
- b. Seizure semiology:

	no	Yes, not specified	Bilateral, symmetric	Bilateral, asymmetric	Unilateral, focal	Unilateral, Hemi
Epileptic spasms						
Tonic						
Clonic						
Tonic Clonic						
Myoclonic-Tonic						
Myoclonic						
Myoclonic-Atonic						
Absence						
Atonic/Drop-attack						
Arrest/Staring/Blinking seizures						
Other Focal Motor						
Sensory/Autonomic						

- 3. Date of postneonatal epilepsy diagnosis:
- 4. Postneonatal epilepsy diagnosis:
 - a. No postneonatal epilepsy
 - b. Infantile spasms
 - c. Focal epilepsy related to structural brain injury
 - d. Focal epilepsy, cause unknown
 - e. Generalized epilepsy related to structural brain injury
 - f. Generalized epilepsy, cause unknown
- 5. Epilepsy treatments prescribed (list all that apply):

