Plan for developing a formal study protocol [RQ-2]. The co-PIs will finalize the draft of the Manual of Operations, clinical research forms, and consent forms during the first month of the study period. Site investigators from participating centers and our Parent Partners will be invited to provide feedback in writing and/or during a teleconference, and the PIs will incorporate this feedback prior to finalizing the documents. For the parent and family well-being aim (Aim 3), our co-investigator [name] will work with our Parent Partners to refine the co-developed protocol for measuring parent and family psychosocial dimensions, including administering the validated instruments at the time of initial hospital discharge and at the 12-month, 18-month, and 24-month follow-ups.

Study Procedures (Table 1). (1) Neonatal Clinical Data. Clinical and demographic data will be collected from the hospital charts during the neonatal admission (Appendix 1). (2) Follow-up Outpatient EEG. A 1-hour EEG will be obtained at 2-4 months corrected age, and two investigators who are blinded to treatment duration and outcome will score the studies according to published criteria^{24,25} (Appendix 2). (3) Follow Up. A trained member of the study team, who is blinded to treatment duration, will contact families to administer a validated follow-up instrument to measure functional developmental outcome (The Warner Initial Developmental Evaluation of Adaptive and Functional Skills (WIDEA FS)) and follow-up questionnaires to determine the rates and types of epilepsy at 12, 18, & 24 months old(Appendices 3 & 4). (4) Parent and family well-being. Validated instruments to measure selected dimensions of well-being and open-ended free-text guestions specific to the impact of anticonvulsant treatment impact on parents and families will be administered at the time of hospital discharge and concurrent with the other assessments (Appendix 5).
Table 1: Study Procedures and Measurements.

Study Measurements	Examples			
Neonatal Clinical Data (Appendix 1)				
- Demographics	Sex, birth weight, gestational age at birth, mode of delivery, etc.			
- Seizure etiology	HIE/ischemic stroke/intracranial hemorrhage/intracranial infection/other (based on chart review and neuroimaging findings)			
- Seizure characteristics	Presence and frequency of electrographic seizures, including presence of status epilepticus			

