- Medications administered	Type, dose and timing of each seizure medication during the admission and at the time of discharge home Medication duration measured as short (discontinued prior to or at discharge) vs. prolonged (discontinued after discharge)			
3-Month Follow Up (Appendix 2)				
- 1 hr outpatient EEG	Scored by 2 independent EEG reviewers, blinded to patient history			
12-18- & 24-Month Follow Ups (Appendices 3 & 4)				
- Functional neurological score	Warner Initial Developmental Evaluation of Adaptive and Functional Skills (WIDEA FS) administered by telephone			
- Epilepsy evaluation	Epilepsy assessment instrument and modified Engel classification (administered by telephone); epilepsy syndrome characteristics and treatment confirmed through medical record review			
Parent Surveys (Appendix 5)				
- Parent and family well-being measurement	A suite of validated instruments and open-ended free-text questions were selected in partnership with our Parent Partners. These will be administered at the time of hospital discharge and at the 12-month, 18-month, and 24-month follow-up.			

Selection of comparators [RQ-5]. The primary comparator will be duration of medication use for the treatment of acute symptomatic seizures.

- As described in our analysis below, we will examine duration of phenobarbital as follows:
 - Treatment as a dichotomous predictor (short versus prolonged, Aims 1 & 3)
 - Treatment as a continuous predictor (Aim 2)

Preliminary data from the *Neonatal Seizure Registry* support two main patterns of treatment, which will be our comparators:

- 1. Short duration phenobarbital: Discontinuation of phenobarbital for acute
- symptomatic neonatal seizures prior to discharge home.
- 2. Prolonged duration phenobarbital: Continuation of phenobarbital for acute symptomatic neonatal seizures until outpatient follow-up (age 2-4 months).

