Therefore, assessment of the incidence of epilepsy, and potential predictors of epilepsy, are priorities for this application. As part of the 12-month, 18-month, and 24-month assessments, parents of enrolled infants will be asked a series of questions designed to discern if the child has developed epilepsy, and if so, what type of epilepsy. Medical records will be reviewed in order to extract detailed data regarding epilepsy syndromes and treatments. All infants will undergo a follow-up 1-hour EEG when they are 2-4 months old. Two board-certified clinical neurophysiologists (Drs. [name] and [name]) who are blinded to the neonatal seizure treatment duration will score the EEG recordings using well-defined, standardized variables (**Appendix 2**), with differences resolved by consensus. The EEG results will be included in the statistical modeling of potential predictors of epilepsy. The study investigators who ascertain the epilepsy and EEG outcomes will be blinded to the treatment group.

b) Length of stay (Aim 2) is an important outcome for parents, clinicians and insurance providers. Said one parent: *"Every additional minute in the hospital... feels like an eternity... The sooner you get home, the better."* Preliminary data from the *Neonatal Seizure Registry* suggest a trend toward longer length of stay among newborns who were discharged home with medication (p=0.1).

c) Parent and family well-being (Aim 3, **PC-3**). Our Parent Partners selected the hospital discharge and 12, 18, and 24-month instruments during focus groups co-led by a study co-investigator who has extensive experience in parent engagement in research ([name]) and a lead Parent Partner ([name]). The Parent Partners discussed the most relevant domains of family well-being, reviewed the pertinent validated instruments (*e.g.* measures of quality of life, anxiety and depression, family coping, parent post-traumatic stress and post-traumatic growth, parenting confidence and competence, and family functioning), and then selected the most

PCORI Research Plan version 2 8/1/2016

relevant and valid measures (see **Appendix 5**). Questions specific to the impact of seizure medication on family well-being were developed together by the Parent Partners and investigators (see **Appendix 5**).

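### The telephone epilepsy form has the blinded caller ask about the treatment group before the seizure outcomes

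*Combined protocol and SAP*

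**What the plan says.** Study Procedures, item (3), describes the follow-up calls: "A trained member of the study team, who is blinded to treatment duration, will contact families to administer a validated follow-up instrument". The same sentence gives that person the epilepsy questionnaire as well, at 12, 18 and 24 months. The section on the primary outcome repeats that the WIDEA FS examiner is blinded. The section on epilepsy as a secondary outcome states: "The study investigators who ascertain the epilepsy and EEG outcomes will be blinded to the treatment group".

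Table 1 defines the exposure: "Medication duration measured as short (discontinued prior to or at discharge) vs. prolonged (discontinued after discharge". It describes the epilepsy evaluation as "Epilepsy assessment instrument and modified Engel classification (administered by telephone); epilepsy syndrome characteristics and treatment confirmed through medical record review".

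Appendix 4 is the telephone questionnaire for Aim 1b. Its item 2 asks "If your child was treated with medicine for neonatal seizures, did he/she ever stop taking this medicine". The first two answers are "Yes, before we left the hospital" and "Yes, after we left the hospital"; the others are No and Don't know.

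The section on developing the formal protocol says that the co-PIs "will finalize the draft of the Manual of Operations, clinical research forms, and consent forms during the first month", so Appendix 4 is presented as a draft.

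**The concern.** The form makes the caller ask for, and write down, the fact to which the caller is supposed to be blind. It does so just before the questions that establish whether the child had seizures after going home.

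This is an unrandomised non-inferiority comparison in which the parents who supply the answers know the treatment. Blinding of the person who elicits and records those answers is one of the few protections against differential ascertainment that the plan can control, and the plan claims it for both Aim 1 outcomes. If the form is used as drafted, the claim is untrue for the epilepsy interview and unsecured for the primary outcome.

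**Working it through.** The question is one of consistency between passages; the only arithmetic concerns how closely item 2 matches the exposure.

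**1. Does item 2 reveal the group?** Set against the Table 1 definition:

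| Item 2 answer | Group indicated |
|---|---|
| a. Stopped before leaving hospital | Short |
| b. Stopped after leaving hospital | Prolonged |
| c. Never stopped | Prolonged |
| d. Don't know | Not revealed |

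Three of the four answers indicate a group.

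**2. Where does it fall in the interview?** The order is:

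- item 1, neonatal seizures
- item 2, when medicine stopped
- item 3, seizures after going home
- item 4, age at onset
- item 5, current frequency
- item 6, infantile spasms
- item 7, current medication

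The only skip instruction follows item 3, so no family reached by telephone bypasses item 2. Every question on later seizures comes after it. A No at item 3 fixes the answer to item 5 and ends the call.

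**3. Is there a safeguard elsewhere?** None is stated. No section gives item 2 to a second person, moves it to the end, or says how blinding is kept once it has been answered.

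**4. How close is the match if exposure means phenobarbital?** Table 1 speaks of medication, and on that wording an accurate answer a, b or c gives the group directly. The comparators are defined by phenobarbital, whereas item 2 says medicine. The registry figures under the preliminary data on practice heterogeneity are 306 infants, 77% sent home on medication, and phenobarbital prescribed to 89% of those.

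- Sent home on another medicine only: 0.77 × (1 − 0.89) = 0.77 × 0.11 = 0.0847, about 8.5% (306 × 0.0847 ≈ 26 infants).
- Accurate answer a, b or c matches the phenobarbital group: 1 − 0.0847 = 0.915, about 91.5%.
- With the planned split in the sample size section (210 of 300 prolonged, or 0.70) in place of 77%: 0.70 × 0.11 = 0.077, giving 92.3%.

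**5. Does it reach the WIDEA FS?** This is conditional. One caller role gives both instruments, the order within a call is not fixed, and nothing says that callers change between ages. Study Procedures and Appendix 6 both list the WIDEA FS first, so a first call could be scored blind. A caller who asked item 2 first, or who asked it at 12 or 18 months, would know the group before the 24-month WIDEA FS, which Potential participant subgroups identifies as the primary outcome.

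**6. Is item 2 needed?** Table 1 takes medication data from the admission and discharge record, and the Missing data section expects under 1% missing for seizure medication at discharge. The preterm analysis uses days of treatment, but item 2 records no date or number of days. No stated analysis uses its answer.

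**The case against.** The strongest reply is that the demonstrated fault touches one source for a secondary outcome. Epilepsy is also ascertained from medical records, and the blinding statement in the epilepsy section refers to investigators, who need not be the callers. This is fair as to consequence, and it limits how far that statement is contradicted. It does not rescue Study Procedures, which calls the caller blinded in so many words. Whether record review is itself blinded is a separate matter.

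Second, the risk to the WIDEA FS depends on call order and on callers returning, neither of which is stated, and its items are fixed four-level parent reports that leave limited room for caller judgement. That stands, which is why the conclusion there is only that blinding is not secured.

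Third, removing item 2 would not guarantee blinding. Site predicts treatment strongly (3% to 75% stopped before discharge), coordinators are in contact with families, and item 7 asks about current medicines. This also stands, but other possible leaks do not justify a form that discloses the group by design.

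Fourth, item 2 is not wholly redundant. It is the only structured question in the Aim 1 forms shown that separates stopping later from never stopping. That distinction lies within the prolonged group, and it can be collected elsewhere.

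Finally, the form was a draft. The conclusion therefore applies only if it is used as printed.

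**Conclusion.** The concern holds. With Appendix 4 as drafted, the epilepsy interview cannot be blinded to treatment duration as Study Procedures states, nor as the epilepsy section states so far as epilepsy is ascertained by that interview. Confidence in this part is high. For the 24-month WIDEA FS the plan leaves blinding unprotected, without showing that it would be lost.

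The match between item 2 and the group is direct under the Table 1 wording and about 91.5% under the phenobarbital definition. The latter assumes accurate parental answers, sets Don't know aside, and carries registry proportions over to the study. It measures disclosure, not bias; the documents support no estimate of bias size or direction. Every family here means every family reached by telephone.

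**What to change.** - Remove item 2 from the outcome caller's script and classify short versus prolonged from the discharge medication record.
- If the distinction between stopping later and never stopping is wanted, add a structured item to the self-completed Aim 3 survey, whose 12-month open-ended questions already touch on continued medication. Alternatively, use a chart field completed by someone who does not classify epilepsy.
- State in the Manual of Operations that the WIDEA FS is completed before any seizure or medication question in each call.
- If item 2 stays, stop describing the epilepsy interview as blinded, and describe the WIDEA FS as blinded only for calls in which the caller had not already heard the answer.

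The document shows a last IRB approval of 04/20/2020, so the form may already have been in use. In that case the change can protect only the remaining calls, and completed calls should be reported under the last of these points.

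The cost is a minor form revision and perhaps one survey item or chart field, with no extra visits or staff.

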Appendix 6: Standards for Data Registries [DR-1 to DR-3]

Patient Follow-up will be at pre-specified ages as outlined in the proposal. The initial follow-up (2-4 month EEG) will be arranged at the time of enrollment for the N=150 prospectively enrolled infants. The Aim1 12-month, 18-month, and 24-month follow-up assessments for all participants will be conducted by telephone and will include:

- WIDEA FS (functional neurodevelopmental outcome, which is the primary endpoint, Appendix 3)
- Epilepsy assessment (Appendix 4)

As requested by our Parent Partner Advisory Panel, participating families may complete 12-month follow-up family wellbeing assessment for Aim 3 either by mail (paper copies of the questionnaires) or via online questionnaire administration (**Appendix 5**).

The 24-month contact is planned to be the last contact with patients and their families.

Adequacy of Follow-Up Duration: 24-month follow-up is both scientifically justified and practical. By 12 months, those with significant developmental delays can be identified using standard neurodevelopmental assessment instruments, such as the WIDEA FS. Additionally, those with the most severe forms of post-neonatal epilepsy, such as infantile spasms, typically present before the child's first birthday. Although more subtle developmental differences may emerge later, in school age children, longer follow-up is not feasible within a 3-year grant cycle. We plan to request permission from enrolled families to contact them at a later date for long-term outcome assessment, once additional funding is secured.

Retention and Expected Loss to Follow-Up: We anticipate excellent retention, since all neonates enrolled in this study will have close clinical follow-up with the study centers through a high-risk developmental follow-up program, pediatric neurology, and/or pediatric epilepsy. We have designed the protocol to avoid unnecessary travel to the study centers. The follow-up EEG will be recorded between ages 2 and 4 months, a timeframe during which typical neurology clinical assessments are scheduled. The assessments will be conducted via telephone interview (Aim 1), and online or by mail (Aim 3), rather than in-person evaluations. Despite this, we have accounted for a 15% loss to follow-up in our analysis plan.

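### Appendix 4 asks about infantile spasms and current seizure medication only of parents who have already reported seizures, so neither item can catch a mistaken 'No'

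*Combined protocol and SAP*

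**What the plan says.** Appendix 4 of the combined protocol and SAP has two parts: a parent telephone questionnaire and a set of medical-record items.

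- Item 2, put to every family: "If your child was treated with medicine for neonatal seizures, did he/she ever stop taking this medicine". The options separate stopping before leaving hospital, stopping afterwards, and never stopping.
- Item 3: "After you went home from that admission, did your child ever have more seizures". The options are Yes, No and Don't know.
- The instruction after item 3, for a 'No': "then indicate answer 'a' for question 5 and end telephone survey". Only a 'Yes' is told to go on. Answer a at item 5 is a positive statement that there have been no seizures since the newborn period.
- Item 6: "Has your child ever been diagnosed with infantile spasms (a particular kind of epilepsy"
- Item 7: "Is your child taking medication for seizures now"

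The record part opens with "Did the child remain seizure-free after discharge from the admission during which neonatal seizures were diagnosed". It has an epileptic-spasms row for seizure type, an infantile-spasms diagnosis option and a list of treatments prescribed. The outcome-selection text, Table 1 and the Scales and tests section all describe record review as part of the epilepsy assessment.

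**The concern.** Item 6 is the only telephone item that names infantile spasms and tells the parent that they are a form of epilepsy. A parent who does not count spasms as seizures could answer 'No' at item 3. The form then records a definite absence of seizures and closes before the item that might have prompted a correction. Item 7 could also raise doubt about a 'No', by showing that the child is on a seizure medicine, and it is skipped at the same point.

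Epilepsy is the Aim 1b outcome. Appendix 6 partly defends the follow-up duration on the ground that "those with the most severe forms of post-neonatal epilepsy, such as infantile spasms, typically present before the child's first birthday", and 2 of the 6 epilepsy cases in the pilot (Table 2) were infantile spasms, though these are small numbers. Aim 1b is a non-inferiority comparison, in which missed cases tend to favour the hypothesis of no difference.

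**Working it through.** **Routing.** The plan gives no ascertainment figure to reproduce, so the first check is the path through the form.

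| Answer at item 3 | What follows | Items 6 and 7 asked? |
|---|---|---|
| Yes | Items 4 to 7 | Yes |
| No | Item 5 coded a, questionnaire ends | No |
| Don't know | No instruction | Undefined |

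Neither item 6 nor item 7 appears earlier in the form. The stop applies at each contact (12, 18 and 24 months), so a later 'Yes' would open both items.

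**What the other items cover.** Item 2 comes before the stop. It shows whether the neonatal medicine was stopped, and whether that was before or after discharge. It does not show a medicine that was restarted or a different one begun later. The record items can show a spasms diagnosis and treatments prescribed, and nothing makes them conditional on item 3. A case is therefore lost only if the parent answers 'No' at every contact and the site's records do not show the diagnosis.

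**Number of families on the short path.** Inputs from Sample Size Calculations: 300 children, 15% loss to follow-up, 20% epilepsy incidence.
- Followed: 300 × 0.85 = 255.
- Without epilepsy: 255 × 0.80 = 204. For nearly all of these the skip is harmless, because 'No' is true.
- With epilepsy: 255 × 0.20 = 51. At an assumed 10% missed by both sources, 51 × 0.10 ≈ 5 children.

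**Effect on the comparison.** Let p be true incidence and s the share of true cases detected by call and record together, with no false positives (assumption). The measured difference, short minus prolonged, is s_short × p_short − s_prolonged × p_prolonged.

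Equal misses, true difference at the plan's 13-point limit:
- s = 0.95: 13 × 0.95 = 12.35, about 12.4 points.
- s = 0.90: 13 × 0.90 = 11.7 points.
- s = 0.80: 13 × 0.80 = 10.4 points.

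Equal misses with no true difference leave the difference at zero.

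Misses in the short-duration group only, true incidence 20% in both groups, s_short = 0.90: (0.90 × 20) − 20 = −2 points, in favour of short duration.

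The values of s are illustrative; the documents give no estimate.

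**The case against.** The strongest reply is that epilepsy is not coded from the telephone call alone. Record review is planned and can be completed for a child whose parent answered 'No'. Appendix 6 expects an epilepsy diagnosis to be readily apparent in the electronic record when a family cannot be reached, and these children are followed through neurology or high-risk clinics. Item 6 also asks about a diagnosis already made, so it would not find unrecognised spasms. No document text shows that parents deny seizures after such a diagnosis. All of this stands, and it makes the added yield narrow.

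It does not close the gap. Table 1 and the outcome-selection text describe the record mainly as confirming or detailing syndromes and treatments. The section on barriers to recruitment says that some sites draw families from long distances, so care given elsewhere may not be visible to the site. No rule says which source prevails when the call is coded as no seizures and the record is silent or disagrees.

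Three stronger readings are tempting, and the documents do not support them.
- A reader might infer that infantile spasms will go unascertained. Record review is a direct route to that diagnosis.
- A reader might infer that the skip hides how long the prolonged group was treated. Item 2 is asked before the stop, item 7 collects no stop date, and the Aim 1 exposure is set by medication status at discharge.
- A reader might set a 2-point fall in overall incidence (10% of 20%) against the 13-point limit. The limit applies to a between-group difference. With equal 10% misses, a true 13-point difference shifts by 1.3 points (13 − 11.7), and a null difference does not shift.

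**Conclusion.** The routing defect is established on the text: items 6 and 7 cannot correct a mistaken 'No', and 'Don't know' at item 3 has no route. The consequence is limited to diagnoses, or restarted or new treatments, that the site's records do not show. How many there would be is unknown.

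If misses are equal, a true difference is diluted towards none, for example from 13 to 11.7 points at an assumed 10% miss rate. If they are commoner in the group discharged off medication, the bias favours that group in the non-inferiority comparison. Appendix 6 itself raises the possibility that these infants are more often lost to follow-up, because they need no prescription refills. It adds that, in the team's experience, their families do want to return at 2 to 4 months. Unequal ascertainment is therefore plausible but not shown.

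The primary outcome and the stated sample size and power figures are unaffected. This is a minor point about a secondary outcome, worth acting on because the remedy is nearly free.

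**What to change.** Change the instruction after item 3. On 'No' or 'Don't know', ask items 6 and 7 and then end the questionnaire. If either answer is 'Yes', or the call and the record disagree, require record review before the child is coded as having no epilepsy. Because the remaining risk lies in care recorded elsewhere, that review should include asking for the outside record where the parent names one. A 'Yes' at item 7 is not evidence of epilepsy in itself, since it may mean only that the neonatal medicine continues; read it alongside item 2. State which source prevails if the conflict cannot be resolved.

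The cost is a form edit, two existing questions added to a call already being made, and record checks for the few children flagged. Added unblinding of the interviewer is small, because item 2 already asks whether medication was stopped before or after leaving hospital.
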